9.7 Sample size calculation

An overall type I error (2-sided) 5% will be used to control type I error. A total of 279 subjects per each group is deemed appropriate to achieve adequate power for the primary and secondary endpoints for this study.

Based on the modeling of Secukinumab data from an unpublished non-interventional study that did a blinded re-read of radiographic X-ray images from a Secukinumab phase III study ([Braun](#)

[REDACTED]

2016) and from a historical cohort where subjects took NSAIDs, a no progression rate of 66% for Secukinumab-treated subjects and 51% for NSAIDs-treated subjects at Week 104 were calculated. Published data for anti-TNFs compared to a cohort of subjects who took NSAID showed no difference in change from baseline in mSASSS at Week 104 (van der Heijde 2009). Therefore, the 51% no progression rate calculated from the subjects who took NSAIDs will be used for GP2017. Assuming 80% of subjects will complete the 2-year study treatment period and provide both baseline and Week 104 evaluable radiographic films with 66% no progression rate at Week 104 and assuming for subjects who discontinue study treatment with 51% no progression rate at Week 104, a new no progression rate of 63% for Secukinumab was calculated using the definition of the estimand. Therefore, no progression rate of 63% for secukinumab and 51% for GP2017 were used as assumptions to calculate the sample size using a two-group Chi-square test of equal proportion (nQuery Advisor 7.0). This calculated approximately 73% power at $\alpha=0.025$ for each secukinumab dose, and the power to reject at least one of these hypotheses using the Hochberg procedure is 88% at an overall type I error of 5%.

Analysis of an unpublished Phase III study showed a change from baseline in mSASSS at Week 104 with a mean of 0.52 and standard deviation of 2.5 for Secukinumab subjects. With a sample size of 279 subjects in each treatment group, a treatment difference of 0.58 (i.e. assuming GP2017 have a mean of 1.1 and the same standard deviation) yields approximately 68% power at $\alpha = 0.025$.

Analysis of an unpublished Phase III study showed the 68% of the randomized subjects have syndesmophyte at baseline and for this subset the proportion of subjects with no new syndesmophyte at Week 104 is 70% for Secukinumab. With a sample size of 190 subjects in each treatment group (about 68% of the planned randomized 279 subjects), a treatment difference of 15% (i.e. assuming GP2017 response rate of 55%) yields approximately 78% power at $\alpha = 0.025$.

10 Ethical considerations

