9.5 Analysis of secondary variables

9.5.1 Efficacy variables

The secondary efficacy variables and the method for adjusting for multiplicity are described below. Handling of missing data for secondary variables included in the testing strategy will be the same as for the primary variable. All analysis will be done on the FAS.

Modified Stoke Ankylosing Spondylitis Spine Score (mSASSS) at Week 104

Change from baseline in mSASSS will be evaluated using ANCOVA model with treatment as a factor and baseline mSASSS as a covariate.

Estimand definition:

- Population – defined through appropriate inclusion/exclusion criteria to reflect the targeted AS population
- Variable – mSASSS change from baseline at Week 104
- Intercurrent event – regardless of adherence to randomized treatment
- Population-level summary – difference in means between treatment

New syndesmophytes at Week 104

The proportion of subjects with no new syndesmophyte will be evaluated using a logistic regression model with treatment group as a factor and baseline mSASSS as a covariate. Difference in marginal response proportions with p-value and respective 95% confidence interval will be estimated from the logistic regression model.

Estimand definition:

- Population – defined through subjects with syndesmophyte at baseline, within the targeted AS population defined by inclusion/exclusion criteria
- Variable – binary response variable indicating absence of new syndesmophyte at Week 104. Absence of new syndesmophyte is defined as having individual vertebral score < 2 for all interpretable locations which had no syndesmophyte at baseline
- Intercurrent event – regardless of adherence to randomized treatment
- Population-level summary – difference in proportion of absence of new syndesmophyte between the secukinumab and GP2017 arms

MRI of spine and SI joints

MRI analysis will be based on a subgroup of subjects who have MRI performed on spine and SI joints at selected sites.

The change from baseline to Week 104 in ASspiMRI-a Berlin modification score and Berlin SI joint edema score will be evaluated using a non-parametric ANCOVA model with treatment as factor and baseline score as covariate. Pairwise comparison will be performed for secukinumab (150 mg s.c. or 300 mg s.c.) versus GP2017. These will be assessed and analyzed outside the testing strategy.

If values are missing for baseline or post-baseline visit, the subject will be excluded from the analysis.

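### Are the stated powers for the two tested secondary endpoints too high because only the primary was diluted for treatment discontinuation?

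*Protocol*

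**What the plan says.** For the primary, Protocol 9.7 starts from no-progression rates of 66% on secukinumab and 51% on GP2017. It then allows for subjects who stop: "Assuming 80% of subjects will complete the 2-year study treatment period". Those who discontinue are given the 51% rate, and "a new no progression rate of 63% for Secukinumab was calculated using the definition of the estimand". The 63% against 51% comparison gives the stated 73% power at alpha 0.025.

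The secondary inputs come from an unpublished Phase III study. The mSASSS change is entered "with a mean of 0.52 and standard deviation of 2.5 for Secukinumab subjects"; with 279 per group, "a treatment difference of 0.58 (i.e. assuming GP2017 have a mean of 1.1 and the same standard deviation) yields approximately 68% power". For syndesmophytes, "for this subset the proportion of subjects with no new syndesmophyte at Week 104 is 70% for Secukinumab", and with 190 per group "a treatment difference of 15% (i.e. assuming GP2017 response rate of 55%) yields approximately 78% power". No discontinuation step appears for either. SAP 3 repeats all three calculations in substance.

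Protocol 9.5.1 gives both tested secondaries the same intercurrent-event strategy as the primary, "regardless of adherence to randomized treatment". It adds: "All analysis will be done on the FAS".

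**The concern.** The reason given for diluting the primary seems to apply equally to the secondaries. All three analyses keep subjects who stop treatment, yet only the primary effect is reduced for them. A reader who sees 73%, 68% and 78% in one section will take them to be comparable. They may not be: without its dilution step the primary's 73% would be about 91%.

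Both documents call 279 per group adequate for primary and secondary endpoints. If 0.52 and 70% were on-treatment or completer values, that statement would rest on secondary powers 21 to 22 points too high under the primary's mix. A non-significant secondary result would then be easier to attribute to low power than the plan suggests.

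**Working it through.** **Inputs** (Protocol 9.7; same values in SAP 3). Two-sided alpha 0.025, critical z = 2.241. Primary: n = 279 per group, 66% and 51%, 80% completing treatment. mSASSS change: n = 279, means 0.52 and 1.1, SD 2.5. Syndesmophytes: n = 190 (0.68 × 279 = 189.7), 70% and 55%.

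**Formulas.** Proportions: power = Φ{(|p₁ − p₀| − 2.241·s₀)/s₁}, with s₀ = √[2p̄(1 − p̄)/n], p̄ = (p₁ + p₀)/2, and s₁ = √{[p₁(1 − p₁) + p₀(1 − p₀)]/n}. Means: two-sample t-test with noncentrality δ/(SD·√(2/n)).

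**Step 1: the plan's own figures.**

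- Primary: 0.8 × 66% + 0.2 × 51% = 63.0%. Then s₀ = 0.0419, s₁ = 0.0416, power = Φ(0.626) = 73.4% (stated 73%).
- mSASSS change: noncentrality 0.58/(2.5 × √(2/279)) = 2.740, power 68.9% (stated 68%).
- Syndesmophytes: s₀ = 0.0497, s₁ = 0.0491, power = Φ(0.788) = 78.5% (stated 78%).

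At two-sided 0.05 the secondaries would be about 78% and 86%. The stated figures therefore use 0.025 and the undiluted differences.

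**Step 2: the conditional loss.** Suppose 0.52 and 70% are on-treatment values and subjects who stop take the GP2017 mean or rate.

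- mSASSS change: 0.8 × 0.52 + 0.2 × 1.1 = 0.636; difference 1.1 − 0.636 = 0.464.
- Syndesmophytes: 0.8 × 70% + 0.2 × 55% = 67%.

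The 10% row below is a milder case. Under the linear time trend of SAP 2.6.3, with stopping times uniform over two years (an assumption), a subject who stops is off treatment for half the follow-up on average, so 20% × ½ = 10% effective dilution: 0.9 × 0.58 = 0.522. For syndesmophytes, 10% is an illustration only: 0.9 × 70% + 0.1 × 55% = 68.5%.

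| Effective dilution | mSASSS difference | Power | Syndesmophytes | Power |
|---|---|---|---|---|
| 0% (as stated) | 0.58 | 69% | 70% vs 55% | 78% |
| 10% | 0.522 | 59% | 68.5% vs 55% | 68% |
| 20% | 0.464 | 48% | 67% vs 55% | 56% |

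For comparison, the undiluted primary (66% vs 51%) has power Φ(1.370) = 91.5%.

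**Step 3: the other reading.** If 0.52 and 70% already contain 20% who stopped, under the same mix, the loss is zero. The on-treatment values behind them would be 1.1 − 0.58/0.8 = 0.375 and 55% + 15%/0.8 = 73.75%.

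**Step 4: what the documents say about which reading applies.** The 66% comes from modelling a blinded re-read and is tied explicitly to subjects who complete treatment with evaluable films. The 0.52 and 70% are reported from analysis of a Phase III study, with no mention of completers. The 70% follows directly on a statement about the share of randomized subjects with a baseline syndesmophyte. That leans towards an all-randomized basis but does not establish it. Protocol 1.1 also cites a two-year secukinumab mean change of about 0.3, so 0.52 may already be cautious. Diluting 0.3 gives 0.8 × 0.3 + 0.2 × 1.1 = 0.46, a difference of 0.64 and power of 78%, above the stated 68%. This is not decisive either: the same section gives 0.8 to 0.9 for progression on anti-TNF, and with those values the diluted difference is only 0.8 × (0.8 − 0.3) = 0.40 to 0.8 × (0.9 − 0.3) = 0.48.

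**The case for a change.** The strongest case for a change is that the sponsor itself justified the dilution by the estimand, and that the secondaries share the treatment-policy strategy and keep subjects who stop. The primary's 66% also traces back to a secukinumab Phase III study and was still diluted, so a similar source does not explain the difference in handling. The sentences are complete in both documents, so redaction is no explanation. One clarifying sentence would settle the matter.

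The inconsistency in presentation stands, and so does the silence about the source. The rest is conditional. Nothing in either document identifies 0.52 or 70% as completer values. The 80/20 mix is stated once, for a binary primary. Carried over to mSASSS change, it gives the full GP2017 mean even to a subject who stops shortly before Week 104. The 20% rate within the syndesmophyte subset is also an assumption. Only the intercurrent-event strategy is shared: the variables differ, and so does the population for syndesmophytes.

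**Conclusion.** No change follows. Each stated power is correct for its stated inputs, to within about one point. Whether those inputs need dilution depends on a source outside the documents. The possible loss runs from zero, if 0.52 and 70% include subjects who stopped, to about 21 and 22 points, if they are on-treatment values, 20% stop, and all who stop take GP2017 outcomes.

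Even the worst case would alter no decision. The group size was calculated from the primary comparison; the secondary figures only report what 279 per group yields. They are single-test powers at the starting alpha/2. H3 to H6 are tested only after both H1 and H2 are rejected, and alpha can pass between doses, so neither 68% nor 48% is the probability of a secondary success. At the full 0.05 the worst-case figures are 59% and 67%. By Amendment 2 enrollment was complete and all subjects had passed Week 52.

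This is a gap in the description of two planning values. A reader who needs to judge a non-significant secondary result can use the range above: about 48% to 69% for mSASSS change and 56% to 78% for syndesmophytes.

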Summary statistics of observed data by visit and change from baseline will be provided for each treatment regimen. Summary statistics include mean, standard deviation, minimum, lower quartile, median, upper quartile and maximum.

ASAS 20, ASAS 40, ASAS partial remission and ASDAS inactive disease at Week 104

Response at Week 104 to ASAS 20, ASAS 40, ASAS partial remission and ASDAS inactive disease will be evaluated using a logistic regression model with treatment group as a factor and baseline score (if appropriate) as a covariate. These will be assessed and analyzed outside the testing strategy.

Testing strategy

The following hypotheses will be included in the testing strategy, which controls the family-wise two sided type-I-error at 5% level. The two primary hypotheses (H1 and H2) form the first family, which will be tested first at 5% level using the [Hochberg \(1988\)](#) procedure. The second family consists of the secondary hypotheses (H3 through H6), which will be tested only if both primary hypotheses have been rejected, and will be tested at 5% level using the graphical approach for sequentially rejective procedures ([Bretz 2009](#)) as illustrated in [Figure 9-1](#):

Primary hypotheses:

H1: secukinumab 150 mg is not different to GP2017 40 mg with respect to proportion of subjects with no radiographic progression at Week 104

H2: secukinumab 300 mg is not different to GP2017 40 mg with respect to proportion of subjects with no radiographic progression at Week 104

Secondary hypotheses:

[figure not shown]
H3: secukinumab 150 mg is not different to GP2017 40 mg with respect to change from baseline in modified Stoke Ankylosing Spondylitis Spine Score (mSASSS) at Week 104

H4: secukinumab 300 mg is not different to GP2017 40 mg with respect to change from baseline in modified Stoke Ankylosing Spondylitis Spine Score (mSASSS) at Week 104

H5: secukinumab 150 mg is not different to GP2017 40 mg with respect to proportion of subjects with a syndesmophyte at baseline with no new syndesmophytes at Week 104

H6: secukinumab 300 mg is not different to GP2017 40 mg with respect to proportion of subjects with a syndesmophyte at baseline with no new syndesmophytes at Week 104

Figure 9-1 Testing strategy for the second family after both H1 and H2 have been rejected

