The family-wise error rate will be controlled strongly at $\alpha=5\%$ two-sided level with the proposed hierarchical testing strategy. In the first family, the Hochberg procedure will reject H1 and H2, if both of them are significant at level α simultaneously. Otherwise, it will reject H1 if it is significant at level $\alpha/2$, or reject H2 if it is significant at level $\alpha/2$. Because H1 and H2 represent two doses of secukinumab versus GP2017, the correlation between the two test statistics will be positive. In this case, the type I error is controlled for the Simes test ([Sarkar and Chang 1997](#)) and, thus, the family-wise error rate is controlled strongly for the Hochberg procedure.

Once both primary hypotheses within the first family are rejected then the α will be passed to the second family starting with each of the hypotheses H3 and H4 tested simultaneously at $\alpha/2$. Then based on the rejection of one or both (of H3 and H4), the next endpoint will be tested hierarchically for each dose (through H5 and/or H6), respectively. This procedure will continue (pending rejection of the null hypotheses) until H5 and/or H6 are/is rejected respectively, then the respective $\alpha/2$ can be passed on to the other secukinumab regimen's hierarchy of hypotheses in the second family (i.e. H3 or H4), if they are not already rejected at $\alpha/2$. Of note, in the description above, rejection of a hypothesis refers to rejection of the two-sided hypothesis; however the level of a rejected hypothesis is only passed on according to the graphical procedure for the test of another hypothesis if the treatment effect is in favor of secukinumab.

[REDACTED]

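### The 68% and 78% secondary powers are single-test figures; under the plan's own gates the syndesmophyte comparison cannot exceed about 72%

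*Protocol*

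**What the plan says.** Protocol 9.7 opens with the claim that "A total of 279 subjects per each group is deemed appropriate to achieve adequate power for the primary and secondary endpoints for this study"; SAP 3 says the same. Two figures support it for the secondaries that are formally tested, each at alpha 0.025:

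- mSASSS change, 279 per arm: "a treatment difference of 0.58 (i.e. assuming GP2017 have a mean of 1.1 and the same standard deviation) yields approximately 68% power".
- No new syndesmophyte, 190 per arm (the subset with a syndesmophyte at baseline): "a treatment difference of 15% (i.e. assuming GP2017 response rate of 55%) yields approximately 78% power".

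For the primary, the same section gives 73% per dose at alpha 0.025, and 88% for rejecting at least one of H1 and H2 by Hochberg.

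The testing strategy is in Protocol 9.5.1 and SAP 2.6.2. The second family, H3 to H6, is one "which will be tested only if both primary hypotheses have been rejected". Hochberg rejects both primaries when both are significant at the full 5% level. H3 and H4 then start at 0.025 each, and after rejection of one or both, "the next endpoint will be tested hierarchically for each dose (through H5 and/or H6), respectively". Once H5 or H6 is rejected, its alpha passes to the other dose's hierarchy. Alpha is passed on only when the effect favours secukinumab.

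Neither document gives the probability that both primaries are rejected, or any secondary power under this strategy.

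**The concern.** The one power in the plan that reflects multiplicity, 88%, is for rejecting at least one primary. That event does not open the second family; rejecting both does, and it is never quantified. The secondary figures use the split alpha of 0.025, so they allow for two doses but for neither gate.

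The trial is meant to support a label claim on radiographic progression (Protocol 1.2), and 68% and 78% are the only basis for calling the sample size adequate for the secondaries. A reader who takes them as the chance of a confirmatory secondary result will overrate the design. That reader may also take a secondary that was never tested, because a gate closed, as evidence of no effect.

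**Working it through.** **Inputs from the documents.** 1:1:1 allocation, 279 per arm; no progression 63% on each secukinumab dose v 51% on GP2017; mSASSS change 0.52 v 1.1, SD 2.5; no new syndesmophyte 70% v 55%, 190 per arm; family-wise alpha 5% two-sided.

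**1. Reproduce the stated figures as single tests at two-sided 0.025 (z = 2.2414).**

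- Primary, chi-square with pooled null variance. Null SE = √(2 × 0.57 × 0.43 / 279) = 0.04192. Alternative SE = √(0.63 × 0.37/279 + 0.51 × 0.49/279) = 0.04161. Power = Φ((0.12 − 2.2414 × 0.04192)/0.04161) = Φ(0.626) = 73.4% (stated 73%).
- mSASSS change. SE = 2.5 × √(2/279) = 0.2117; noncentrality 0.58/0.2117 = 2.740; noncentral t on 556 df gives 68.9% (stated 68%).
- No new syndesmophyte. Null SE = √(2 × 0.625 × 0.375/190) = 0.04967; alternative SE = √(0.70 × 0.30/190 + 0.55 × 0.45/190) = 0.04907. Power = Φ((0.15 − 2.2414 × 0.04967)/0.04907) = Φ(0.788) = 78.5% (stated 78%).
- At least one primary by Hochberg, exact binomial enumeration: 87.9% (stated 88%).

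All four agree with the plan.

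**2. Probability that the second family opens.** Both z statistics must exceed 1.96, and they share the GP2017 arm. Conditioning on the GP2017 count x₀:

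P(both) = Σ P(x₀) × [P(z > 1.96 | x₀)]², with x₀ ~ Binomial(279, 0.51) and each secukinumab count ~ Binomial(279, 0.63).

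The exact sum is 71.8%. As a check, a bivariate normal has single-test power 81.8% at 0.05 and correlation (0.51 × 0.49)/(0.51 × 0.49 + 0.63 × 0.37) = 0.517; it gives 71.5%.

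**3. The ceiling.** P(gate opens and H5 rejected) ≤ P(gate opens) ≈ 72%. This needs no assumption about correlation, and alpha recycling cannot lift it. Hence 78% is unreachable for H5 or H6. Also, 87.9% − 71.8% = 16.1%: in about one trial in six at least one primary succeeds, yet no secondary is tested.

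**4. Power under the full graph.** Simulation, 2,000,000 trials per setting, shared control, gate at 0.05 for both primaries, H3 and H4 at 0.025, H5 after H3 and H6 after H4, and the other dose's hierarchy at 0.05 once H5 or H6 is rejected. The recycling rule is read from the text because the figure is not shown. The within-patient correlation r between endpoints is not in the documents and is assumed. Because H5 and H6 use 190 of 279 subjects per arm, their test statistics correlate with the others at r × √(190/279) = 0.825r.

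| r (assumed) | H3, one dose | H5, one dose | H3 or H4 | H5 or H6 |
|---|---|---|---|---|
| 0 | 52.2% | 43.2% | 59.6% | 51.4% |
| 0.3 | 55.4% | 48.7% | 62.0% | 56.1% |
| 0.5 | 57.7% | 52.3% | 63.7% | 59.2% |
| 0.7 | 60.5% | 56.3% | 65.6% | 62.3% |

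H4 and H6 match H3 and H5 because both doses have the same assumed effect. Even at r = 0.99, H3 reaches 66.4% and H5 63.8%. Ranges quoted elsewhere are these values rounded down to whole per cent.

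**The case against.** **The figures are right and are labelled.** Each is given at alpha 0.025, the local starting level in the graph. Both gates are set out openly, and quoting local power for secondaries is common practice. This stands: a reader might infer a calculation error, and there is none. It does not rescue the opening sentence of Protocol 9.7 and SAP 3, which uses these figures to claim adequacy for the secondaries without mentioning either gate.

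**The ceiling contradicts only the 78%.** This also stands. The 68% lies below 72%, so the ceiling alone does not exclude it. It is still not the power under the strategy, where H3 stayed below 68% at every correlation tried.

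**The graph figures need a correlation the documents do not give.** True, which is why they are a labelled range. The 72% needs none.

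**Nothing can change now.** All subjects were randomized by Amendment 1. Error control, estimands and analyses are unaffected, so this is a reporting correction.

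**A stronger reading that is not supported.** The primary rate was diluted for discontinuation (0.8 × 66% + 0.2 × 51% = 63%): "a new no progression rate of 63% for Secukinumab was calculated using the definition of the estimand". The secondaries carry the same strategy, "regardless of adherence to randomized treatment", yet 0.52 and 70% are not adjusted. A reader might infer that 68% and 78% are too high even as single tests. The documents do not show this. The secondary inputs come from a differently described analysis of an unpublished Phase III study. Its sentence "showed the 68% of the randomized subjects have syndesmophyte at baseline and for this subset the proportion of subjects with no new syndesmophyte" starts from randomized subjects and may already include those who discontinued. That is at most a question to the sponsor, and no diluted power is offered here.

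**Conclusion.** The concern holds as a matter of what the stated powers mean. The 68% and 78% are correct marginal powers at alpha 0.025, but they do not show that 279 per arm is adequate for secondaries tested behind two gates. The second family opens with probability about 72%. This rests only on the plan's inputs: 63% v 51%, 279 per arm with complete data, a shared control and Hochberg. It rules out 78% for no new syndesmophyte.

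With within-patient correlation assumed between 0 and 0.7, power under the full graph is about 52–60% per dose for H3/H4 and 43–56% per dose for H5/H6; for at least one dose, about 59–65% and 51–62%. The ceiling is firm. The ranges depend on the assumed correlation and on the textual reading of the graph. The point is worth correcting, but it does not threaten the validity of any planned test.

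**What to change.** In Protocol 9.7 and SAP 3:

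1. Label 68% and 78% as marginal powers of a single test at alpha 0.025. Do not call them conditional powers.
2. Add wording such as: *H3 to H6 are tested only if H1 and H2 are both rejected, which has probability about 72% under the primary assumptions with complete data. Under the full testing graph, assuming a within-patient correlation between endpoints of 0 to 0.7 and 190 subjects per arm for H5 and H6, power per dose is about 52–60% for H3/H4 and 43–56% for H5/H6; for at least one dose it is about 59–65% and 51–62%.*
3. Limit the adequacy statement to the primary endpoint, or support it for the secondaries with these figures.
4. Optionally, state whether the 0.52 and 70% inputs include subjects who discontinued treatment.

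The cost is a few sentences and less favourable stated figures. The sample size, testing strategy and analyses do not change.
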